2.3. Benefit/Risk Assessment

Some participants may experience discomfort when completing assessments related to their stress levels and emotional well-being. Although participation in this study may reduce stress and improve emotional well-being, we recognize that individuals experiencing high stress may conversely face the risk of symptomatic worsening. Both text message platforms are two-way. This will allow for review of the evaluation of content and assessment to determine if participants are experiencing a worsening of stress and are in need of further support.

3. Objectives and Endpoints

Objectives	Outcomes

Primary
 
 • Feasibility of recruitment including eligibility rates and acceptance rates • Feasibility of delivering the intervention via text message • Acceptability of the intervention including dropout rates, percentage of completed assessments, adherence, and estimates of satisfaction 	
The main outcome of the FACE STRESS study is to evaluate feasibility and acceptability of an EMA and EMA plus text message intervention. Specifically, we will evaluate:
 
 • proportion of individuals who will contact us because interested to participate • the number of eligible individuals after the initial screening • time taken to recruit the sample • retention rates • the number and percentage of participants responding to any EMA text over the 3-week study • Satisfaction will be measured using both open-ended questions and likert-scaled questions to examine the acceptability and utility of the both EMA and intervention texts.

Secondary
 
 • Explore indicators of the EMA and text message intervention efficacy The effect sizes on reductions in perceived stress and other psychological symptoms will be estimated in the EMA and EMA+intervention groups at post-intervention, 1, 3 and 6-month time-points. 	
Secondary outcomes will measure:
 
 • Perceived stress and psychological overload • symptoms of anxiety and depression • symptoms of PTSD • positive and negative affects • resilience • psychological well-being

4. Study Design

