4.3. End of Study Definition

The end of trial date is defined as the date at which all subjects have completed all activities shown in the Schedule of Assessments, all data has been entered, all data queries have been resolved, and the database has been locked.

5. Study Population

70 participants will be randomized to control (n=35) or intervention group (n=35)

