5.1. Inclusion Criteria

Participants are eligible to be included in the study only if all of the following criteria apply:

1. Age 22 or older
2. Must reside in an Eastern Standard Time or Central Standard Time zone
3. Able to read and write in English as demonstrated by review and completion of an Informed Consent Form
4. Own an SMS enable smartphone (Android or iPhone OS4)
5. Scoring >5 on the 4-item Perceived Stress Scale (reflecting higher-than-average perceived stress; 15, 16)

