8.1. Efficacy Assessments

Participants will be recruited by advertisements posted on an internet job board. Screening assessments will occur remotely via phone to evaluate eligibility.

Planned time points for all efficacy assessments are provided in the SoA.

- **Standard assessment.** Participants will be evaluated at baseline, post-intervention and at 1, 3 and 6 months follow up.
 - Baseline assessment will include:
 - *sociodemographic information* (age, race, gender, employment status, annual income, zip code, living situation, health insurance);

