9.3. Analysis Sets

9.4. Statistical Analyses

Primary outcome.

- *Quantitative analysis.* Feasibility of the intervention will be reported as descriptive statistics, focusing on number of individuals who contact the study team with interest in participation; the number of eligible individuals after the initial screening; time taken to recruit the sample; retention rates; the rate of EMA survey completion. Acceptability will be measured as means and standard deviations of responses to each item within the satisfaction questionnaire, and the proportion of participants giving favorable responses.
- *Qualitative analysis.* A codebook and coding guidelines will be developed for analysis of qualitative feedback. Two researchers will code all transcripts using [REDACTED] and add to the codebook as needed. Each researcher will then independently identify main themes. Results will be compared and discussed until an agreement will be reached. Representative samples of feedback from open-ended questions will be also used.

Secondary outcomes.

- *Standard responses.* Sociodemographic responses will be described by mean, standard deviation (SD), and range. Mixed-effects models for repeated measure (MMRM) will be used to examine change in secondary outcomes, with outcomes examined as change in scores between baseline and follow-up. Models will include effects for time, group (control/intervention), group x time interactions and baseline values of the outcome variable (to control regression to the mean) and other potential confounders. Per Protocol analysis will be performed. The per protocol population will include all randomized participants excluding those who had protocol violations. A significance level of 0.05 will be used. All analyses will be performed using [REDACTED]

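### The secondary-outcome MMRM gives baseline one slope for all four visits; a baseline × visit term is a near-free safeguard against a small bias that arises only under two conditions

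*Combined protocol and SAP*

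**What the plan says.** Section 9.4 (Secondary outcomes) specifies a mixed model for repeated measures "with outcomes examined as change in scores between baseline and follow-up". The fixed effects are given in one sentence: "Models will include effects for time, group (control/intervention), group x time interactions and baseline values of the outcome variable". The purpose of the baseline term follows in brackets, "to control regression to the mean", and the list then closes with further confounders that are not named. Group × time is the only interaction mentioned. The section gives no coding of time, covariance structure or missing-data assumption.

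On timing, section 8.1 says: "Participants will be evaluated at baseline, post-intervention and at 1, 3 and 6 months follow up". That makes four post-baseline visits. The secondary objective in section 3 is that effect sizes "will be estimated in the EMA and EMA+intervention groups at post-intervention, 1, 3 and 6-month time-points".

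Two other provisions matter. Entry requires "Scoring >5 on the 4-item Perceived Stress Scale" (section 5.1), so participants are selected for a high score. Section 9.1 sets a retention criterion of at least 70% but attaches no time point to it.

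**The concern.** A sample selected for high stress will tend to score lower later even with no intervention. The fall is larger, the weaker the correlation between baseline and the later score. If that correlation declines between Day 26 and month 6, the right adjustment for baseline differs by visit. A single slope is then a compromise, too steep early and too shallow late.

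With complete data in a randomised comparison this hardly matters, because baseline is balanced in expectation. It can matter once people drop out: if those remaining at 6 months differ in baseline between arms, a wrong slope leaves part of that difference in the estimated effect. The quantity at stake is the 6-month effect size, one of the secondary estimates from this pilot.

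**Working it through.** **Inputs from the documents.** N = 70, 35 per arm (sections 5 and 9.2); four post-baseline visits (8.1); change from baseline as outcome and the listed fixed effects (9.4). The plan has no figure of its own to reproduce on this point.

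**Assumed inputs.** True effect 0; baseline correlation falling from 0.7 to 0.4, or from 0.65 (or 0.70) to 0.50; about 70% retained at 6 months; monotone dropout depending on baseline only; unstructured covariance fitted by maximum likelihood.

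**Step 1: why two conditions are needed.** In SD units, let the expected score at visit t given baseline B be a_t + ρ_t·B. The change score then has baseline slope β_t = −(1 − ρ_t). For ρ falling from 0.7 to 0.4, β runs from −0.3 at Day 26 to −0.6 at 6 months. In a large simulated sample with about 70% retained, the fitted common slope was −0.37:

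- Day 26: −0.37 − (−0.30) = −0.07, slightly too steep.
- 6 months: −0.37 − (−0.60) = 0.23, too shallow.

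Approximately (the model also borrows from earlier visits),

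bias of the contrast at t ≈ (β_t − β_common) × (difference between arms in mean baseline among those retained).

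The product is zero if the slope does not drift, and zero if retention selects on baseline equally in both arms.

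**Step 2: simulated bias of the 6-month contrast (SD units).** The first set used 500 trials of N=70 per scenario (Monte Carlo error about 0.012). The second used samples of 60,000 to 200,000. Dependence is the log-odds of dropout per SD of baseline.

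| Baseline slope | Dropout dependence | Common slope | With baseline × visit |
|---|---|---|---|
| Constant at 0.6 | none, equal, one arm or opposite | within 0.01 of 0 | within 0.01 of 0 |
| Drifting | no dropout, or equal in both arms | no bias; the two models differ by at most 0.003 | no bias |
| 0.7 to 0.4 | one arm (0.7 or 0.8) | 0.05 to 0.06 | within about 0.02 |
| 0.7 to 0.4 | opposite (±0.5 to ±0.8) | 0.08 to 0.11 | within about 0.02 |
| 0.70 to 0.50 | one arm / opposite | 0.035 / 0.06 | within about 0.01 |
| 0.65 to 0.50 | one arm to opposite | 0.02 to 0.08 | within about 0.02 |

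More extreme inputs give more: 0.14 SD with dependence ±1.5 at 0.7 to 0.4, and 0.16 SD with ±0.8 if the 6-month slope falls to 0.20.

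**Step 3: arm difference confined to the intervention period.** With about 70% still retained at 6 months (simulation error about 0.01; interaction model in brackets):

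- 0.7 to 0.4: one arm 0.023 (0.005); opposite ±0.8 0.035 (0.005).
- 0.65 to 0.50: one arm 0.000 (−0.006); opposite ±0.8 0.010 (−0.004).

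**Step 4: within-arm change at 6 months.** With equal dependence in both arms (0.8) and slopes 0.7 to 0.4, the common slope shifts both arms by 0.043 SD. With baseline × visit the shifts are −0.006 and −0.007.

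**Step 5: size against sampling error.** The standard error of the contrast at N=70 is about 0.25 to 0.29 SD. Taking 0.25:

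- One arm: 0.06 / 0.25 = 0.24 standard errors.
- Opposite: 0.11 / 0.25 = 0.44.
- Intervention period only: 0.04 / 0.25 = 0.16.

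For a two-sided 5% test (9.4 does not state sidedness), a shift of 0.44 gives a false-positive rate of Φ(−1.96 + 0.44) + Φ(−1.96 − 0.44) = 0.064 + 0.008 = 7.2%. A shift of 0.24 gives 0.043 + 0.014 = 5.7%.

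**Step 6: cost of the extra term.** Four slopes instead of one is three parameters. SD of the 6-month estimate at N=70 (slopes 0.7 to 0.4), without and with the term: 0.226 and 0.221 with no dropout; 0.256 and 0.246 with no differential dropout in a separate run; 0.251 and 0.251 with opposite dependence.

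**The case against.** The best defence is that the model is under-specified rather than wrong. A baseline × visit term is left out of the list, not ruled out, and the list ends open. That stands as to tone: a reader might infer that the plan commits itself to a constant slope, and it does not say so. But the open-ended phrase covers further confounders, and a visit-specific slope for a covariate already listed is not a confounder. Fitted as listed, the model has one slope.

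A reader might also infer that the plan promises control of regression to the mean at every visit. It says only that baseline is there to control it, and in a randomised comparison regression to the mean is equal in expectation in both arms.

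The case for arm-different dropout is thin. Under section 4.1 the stress-management texts run only in the last two of the three weeks. Both arms receive the same EMA prompts and, from Day 26, the same follow-up surveys. This is why the figures in step 3 deserve weight. A difference after Day 26 is still possible: there is no blinding (6.3), and only controls are offered the intervention after 6 months (6.6). The documents give no evidence of one, and no reason for dependence in opposite directions, so that scenario is a worst case.

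**Conclusion.** The gap is real and its consequence is small. As listed, the model has a single baseline slope for four visits and cannot track regression to the mean if the association with baseline weakens.

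A reader might conclude that baseline-dependent dropout by itself biases the 6-month group effect. It does not: the slope must drift and the dependence must also differ by arm. When dependence is equal, only the within-arm changes move.

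Under the assumed correlations and retention, bias in the contrast is about 0.02 to 0.06 SD with one-arm dependence, up to about 0.11 SD with opposite dependence, and about 0.01 to 0.04 SD if the arm difference is limited to the intervention period. None of these reaches half a standard error at N=70. Correlations, dropout models and the 6-month reading of the 70% criterion are all assumptions. Whether the slope drifts for each secondary scale is unknown. The primary outcome is descriptive and unaffected. This is an optional improvement.

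**What to change.** In section 9.4, add a baseline × visit interaction to the MMRM, state that visit (post-intervention, 1, 3 and 6 months) is categorical, and report the group difference at each of the four visits from that model.

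The cost is one sentence and three extra parameters per outcome, with no loss of precision in the simulations. Writing it down beforehand also avoids choosing the form of the model after seeing the data.

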4.1. Overall Design

This study is a pilot randomized controlled trial with embedded qualitative research. Eligible participants who complete an informed consent form will be randomized to receive 3 weeks of EMA or 3 weeks of EMA plus the text message intervention for stress management based on a 1:1 allocation using random block sizes of 2.

Eligible participants will sign the consent form online before moving on to complete their baseline assessment. All participants will receive a copy of their signed consent form and will be provided with the research personnel's contact details. Participants who do not complete the baseline survey within 3 days from enrollment will be excluded from the study. Once their baseline is completed, participants will be randomized to receive:

- **Control:** 3 weeks of EMA, consisting of 2 text messages per day delivered at random times during waking hours to prompt participants to complete the survey
- **Intervention:**
 - o 1 week of EMA, consisting of 2 text messages per day delivered at random times during waking hours to prompt participants to complete the survey followed by
 - o 2 additional weeks of EMA in combination with 2 text messages per day with content related to stress management techniques.

At the end of the 3 weeks, participants in both groups will complete a post-intervention survey designed to evaluate participant satisfaction and to gather information for the purposes of improving the content of the text-message intervention. Changes in levels of psychological distress and well-being from baseline will be also evaluated.

At 1, 3 and 6-months post intervention, participants will be contacted via text message to complete a follow up survey. The follow up survey will include the same information collected at baseline with the exclusion of age, race, gender and adverse childhood events.

Participants from either group will be informed that they can withdraw from the study at any time without giving a reason by replying 'STOP' to any of the messages, or by contacting a member of the research team. No further information will be collected from participants who withdraw from the study.

Participants in the control group will be offered the opportunity to receive the intervention after the 6 months follow-up period. No data will be collected from this intervention.

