6.2. Preparation/Handling/Storage/Accountability

Consent and welcome and intervention text messages will be delivered remotely using a web-based SMS messaging platform. To send and receive messages, a third-party web-based text messaging platform was used as the Internet gateway. Participants' cell phone numbers will be registered in the web-based text messaging platform at baseline. EMA and standard surveys will be collected through [REDACTED] a HIPPA approved secure survey platform that enables direct texting. The company is GDPR Compliant; data is stored securely and encrypted in transit, at rest, and on all backups to reduce the risk of data security breach. In addition, the company leverage [REDACTED] security features to further lock down access to data.

Text message send times and delivery status will be recorded. Participants will be informed that this is a one-way message program and not to reply, however record will be kept of any incoming messages from participants. A record of the number of times each participant attempts to contact the research team and the method of contact (i.e. via phone, email, text message) will also be kept.

Participants who text-back will be sent an automated text message as follows ‘From FACE stress: This is an automated reply. If this is an emergency and you are in need of immediate help call 911’. In addition, the content of the message will be reviewed by the research team who will determine an appropriate response including:

- No action required (e.g. text is related to content or acknowledgement)
- Action required on a study-related problem (e.g. participant reporting a technical problem or texting to withdraw from study)
- Action required on a different problem (e.g. text indicating high distress; response will be determined on a case-by-case basis and reviewed by the Principal Investigator and Medical Monitor)

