6.3. Measures to Minimize Bias: Blinding

N/A

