6.4. Study Intervention Compliance

Subjects will receive study intervention via text messages.

Subjects may remain in the trial, even if they are nonadherent with the digital intervention treatment.

A record of the digital intervention administered to each participant will be maintained. Intervention start and stop dates will also be recorded.

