7.2. Participant Discontinuation/Withdrawal from the Study

- A participant may withdraw from the study at any time at his/her own request or may be withdrawn at any time at the discretion of the investigator for safety, behavioral, or compliance reasons. This is expected to be uncommon.
- If a participant withdraws or is withdrawn from the Study, the sponsor will stop collecting new data from the participant, however, the sponsor may retain and continue to use any data collected before the participant withdraws or is withdrawn from the study.
- At the time of discontinuation from the study an early discontinuation visit will be conducted, as shown in the SoA. See SoA for data to be collected at the time of study discontinuation and follow-up and for any further evaluations that need to be completed.

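### The only efficacy population visible for the secondary-outcome MMRM is per protocol, with violations not listed; excluding randomised participants who have outcome data could bias the between-arm effect sizes in either direction

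*Combined protocol and SAP*

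**What the plan says.** Section 9.4 (Secondary outcomes) describes an MMRM on change from baseline, with terms for time, group, group by time, the baseline value and other potential confounders. It then states: "Per Protocol analysis will be performed". The set is defined in the next sentence: "The per protocol population will include all randomized participants excluding those who had protocol violations". The visible text contains no list of violations, no grading of them and no time by which they are to be classified. It names no intention-to-treat or full analysis set. Section 9.3 (Analysis Sets) is a heading with nothing visible under it. Section 9.4.1 refers to a Safety Population that is not defined in the visible text.

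Other sections bear on who might be excluded and what would follow:

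- Section 3, secondary objective: "The effect sizes on reductions in perceived stress and other psychological symptoms will be estimated in the EMA and EMA+intervention groups", at post-intervention and at 1, 3 and 6 months.
- Section 4.1: after one week of EMA alone, the intervention arm receives "2 additional weeks of EMA in combination with 2 text messages per day with content related to stress management techniques". The control arm receives EMA only.
- Section 6.2: "Text message send times and delivery status will be recorded".
- Section 6.3, headed "Measures to Minimize Bias: Blinding", is marked not applicable.
- Section 6.4: "Subjects may remain in the trial, even if they are nonadherent with the digital intervention treatment".
- Section 7.2: after withdrawal no new data are collected, but "the sponsor may retain and continue to use any data collected before the participant withdraws or is withdrawn from the study".
- Section 8: outcomes are self-reported. It also treats adherence to the schedule as mandatory and rules out waivers.

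**The concern.** Randomisation protects the comparison of the arms as assigned. Removing people for events after randomisation protects it only if removal is unrelated to outcome or works alike in both arms. Here there is reason to doubt the second condition. Only the intervention arm receives stress-management texts, so a violation based on their delivery or on exposure to them could occur in that arm alone. The trial is unblinded, outcomes are self-reported, and no visible passage requires violations to be classified before outcomes are seen.

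The definition also leaves room for different analysts to build different sets. Section 6.4 lets nonadherent participants stay in the trial, and section 9.1 sets its feasibility target at only 33% of surveys completed. Both suggest that nonadherence or missed surveys alone are not violations, but neither says so, and the insistence on adherence in section 8 points the other way.

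At stake are the effect sizes at four time points, which are the stated secondary objective, with a 0.05 significance level attached. Bias from exclusion is systematic: it does not show in the confidence interval and does not shrink with a larger sample. The primary feasibility outcomes are not affected.

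**Working it through.** **Inputs from the documents.** 35 randomised per arm (section 5); surveys after baseline at Day 26 and at 1, 3 and 6 months (sections 1.3 and 8.1); an expected effect described as small to moderate, without a number (section 9.2). The plan gives no violation rate and no per-protocol figure, so there is nothing of its own to reproduce.

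**Unequal opportunity for violations.** Assuming EMA stays at 2 prompts a day for 21 days, both arms receive 2 × 21 = 42 prompts. The intervention arm also receives 2 × 14 = 28 stress-management texts, 70 messages in all against 42.

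**Shift from exclusion.** Let f be the fraction excluded among participants with post-baseline data, and d the gap in SD between retained and excluded participants (positive if the excluded do worse). In one arm, the retained mean minus the mean of everyone is f × d. Between arms:

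shift (per protocol minus all randomised) = f_I × d_I − f_C × d_C

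With d assumed to be 0.3 to 0.8 SD and equal in both arms:

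| Net difference in exclusion | Calculation | Shift (SD) |
|---|---|---|
| 5 percentage points | 0.05 × 0.3 to 0.05 × 0.8 | 0.015 to 0.04 |
| 2 of 35 (5.7 points) | 0.0571 × 0.3 to 0.0571 × 0.8 | 0.017 to 0.046 |
| 7 of 35 (20 points, upper end) | 0.20 × 0.3 to 0.20 × 0.8 | 0.06 to 0.16 |
| Equal f and equal d | – | 0 |

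The sign reverses if the excluded do better, or if more are excluded from control.

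**Dependence on which surveys the excluded have.** The table assumes all four post-baseline surveys. If they have only Day 26, the Day 26 shift is unchanged. At later visits the all-randomised MMRM uses their Day 26 value only through its correlation with the later one. With an assumed common correlation of 0.6 between visits, including baseline, the correlation given baseline is (0.6 − 0.36)/(1 − 0.36) = 0.24/0.64 = 0.375. The later shifts are then 0.375 × (0.017 to 0.046) = 0.006 to 0.017 SD for a net 2, and 0.375 × (0.06 to 0.16) = 0.022 to 0.06 SD for a net 7. If they have no post-baseline survey, they contribute nothing under either set and the shift is zero.

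A simulated MMRM agrees (35 per arm, 4 visits, correlation 0.6, 1,500 runs). With 7 v 0 excluded and d = 0.8, the shift is 0.16 at every visit with full data; 0.16 then 0.06 at each later visit with Day 26 only; and 0.00 with no follow-up.

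**Second check, different model.** Let exclusion depend on a latent variable correlated ρ with the outcome residual (positive ρ: violators do worse). Writing r for an arm's exclusion rate, z for the corresponding normal cut-off and φ for the normal density:

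bias = ρ × [φ(z_I)/(1 − r_I) − φ(z_C)/(1 − r_C)]

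Assume a true benefit of 0.20 SD and 35 per arm (4,000 simulated trials):

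| Excluded, intervention v control | ρ = +0.5 | ρ = −0.5 |
|---|---|---|
| 20% v 5% | 0.32 | 0.08 |
| 30% v 10% | 0.35 | 0.06 |
| 10% v 20% | 0.12 | 0.27 |
| 20% v 20% | 0.20 | 0.20 |

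Entries are per-protocol estimates. Analysing everyone randomised gave 0.19 to 0.21 in every case, and ρ = 0 gave no bias.

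**Scale.** The sampling SE of the difference is √(2/35) = 0.239 SD unadjusted, or √(2/35 × 0.64) = 0.191 SD with an assumed baseline correlation of 0.6. If small to moderate means 0.2 to 0.5 SD, a net 2 exclusions is 0.017/0.5 = 3% to 0.046/0.2 = 23% of the effect.

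**The case against.** The strongest objection is that the answer may lie in text that is not visible. Section 9.3 is blank, and section 9.4.1 uses a Safety Population with no visible definition, which suggests that sets were defined somewhere; text removed from the public copy is not missing from the plan. This stands as a limit, and the recommendation is conditional on it. Against it, the per-protocol set is defined in 9.4 itself, and no all-randomised efficacy set is mentioned anywhere else.

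A related objection is that the MMRM is described first without restriction, and the per-protocol sentence may announce an additional analysis. The wording allows this, but no passage says it, so the main population is either per protocol or unstated. One clarifying sentence is needed on either reading.

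The mechanism is also conjectural. No passage makes text delivery a violation, eligibility errors should fall about evenly across arms, and unreachable participants are treated as withdrawn with no further data (sections 4.1, 7.2 and 7.3). That is fair: the concern covers only excluded participants who do have post-baseline surveys, and the documents do not show how many there would be.

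Finally, the illustrated shifts are below sampling error, more so at the 70% retention threshold, where about 24.5 per arm gives √(2/24.5) = 0.29 SD, and efficacy is exploratory. This limits the importance. It does not supply a reason to prefer the per-protocol set.

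**Conclusion.** The concern holds, within those limits. Followed as it stands, the visible text would leave out of the between-arm MMRM randomised participants who have outcome data, on criteria that are not listed. The resulting bias is possible rather than certain, its sign cannot be known in advance, and it is zero if exclusions are alike in both arms, unrelated to outcome, or confined to people with no post-baseline survey.

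Its size in this trial is unknown. The illustrated 0.015 to 0.16 SD at visits where the excluded have data rests on assumed exclusion differences and assumed gaps of 0.3 to 0.8 SD; the later-visit figures also rest on an assumed correlation of 0.6. The point should be fixed because the effect sizes are a stated objective and the remedy is cheap. It does not threaten the trial's main purpose.

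**What to change.** Unless section 9.3 already does so in text that is not visible, state in sections 9.3 and 9.4 that the main secondary-outcome MMRM includes all randomised participants in their assigned arm and uses every available post-baseline survey. Section 7.2 already permits use of data collected before withdrawal.

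Keep per protocol as a sensitivity analysis. List the violations that lead to exclusion, classify them before outcome data are reviewed, and report exclusions by arm with reasons.

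The cost is two or three sentences and no new data collection. The downside is that the main estimate may be diluted compared with one in adherent participants only.
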